9 DEFINITIONS

9.1 Protocol Deviations

Major protocol deviations (PDs) are defined as those deviations from the clinical trial protocol for which there could be a significant influence on the assessment of the treatment efficacy. The impact of major protocol deviations on the efficacy results will be investigated by assessing the robustness of the clinical trial results and conclusions to the choice of analysis population, both

including and excluding data potentially affected by major protocol deviations. Please note that other study documents may refer to the major PDs as important PDs, and minor PDs as non-important PDs. The SAP and TFL shells will be using the terminology major and minor PDs. For the study, a PD List has been pre-specified. The PD list contains the list of all study PDs, the categorization, the criticality [Major (important) or Minor (non-important)], the potential impact on analysis populations. All the processes around the collection and the review of PDs are described in detail in the study PD Management Plan.

9.2 Analysis Data Sets

The term analysis data set is used to define the set of patients to be included in a class of analyses. The analysis data set is described in terms of the specific criteria for patient inclusion.

Eligibility for the analysis data sets will be determined in a blinded Data Review Meeting (DRM) held after closing, but before locking the database and then producing the final analysis. The blinded DRM will be used to determine if patients should be excluded from the Per-Protocol Set (PPS) in cases of significant and major protocol deviations that would interfere with the assessment of treatment efficacy. The protocol deviations and their impact are routinely collected and assessed during the conduct of the study.

9.2.1 Safety Analysis Set (SAF)

The SAF is defined as all randomized patients receiving SoC and/or at least one dose of L-CsA, independently of the treatment allocation at randomization. As per IE criteria, randomized patients should be already in SoC at enrollment, therefore it is expected that all randomized patients will enter the SAF population.

Independently of the treatment allocation at randomization, patients will be analyzed according to the treatment they actually received:

- L-CsA plus SoC group: for all randomized patients receiving at least one dose on IMP (L-CsA);
- SoC group: for all randomized patients not receiving any dose on IMP (L-CsA) but treated with SoC.

All data collected after baseline to the end of clinical trial participation will be included in the safety summaries.

All safety and tolerability data will be summarized and analyzed using the SAF.

9.2.2 Full Analysis Set (FAS)

The FAS is defined as all randomized patients. Patients will be analyzed according to the treatment group to which they were randomized. All primary, **CCI** endpoints will be performed using the FAS, unless otherwise specified.

9.2.3 Per Protocol Set (PPS)

The PPS is defined as all patients included in the FAS

- who complete randomized treatment as scheduled or who are withdrawn prematurely due to lack of efficacy or lack of tolerability of the clinical trial treatment, and
- for whom no major protocol deviations interfering with the assessment of treatment efficacy are observed.

For **CCI** the primary endpoint, the PPS may be used as a supplementary analysis to assess the impact of drop-outs and major protocol deviations on the results.

Lack of efficacy is defined by the withdrawn reason “Lack of efficacy” as collected in the End Of Study CRF form. Lack of tolerability is defined by the withdrawn reason “Adverse Event (Including SAE/Death)” as collected in the End Of Study CRF form.

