## 9.6 Stopping rules and Discontinuation Criteria

### 9.6.1 Patient Level

#### Regular termination of clinical trial participation:

The investigational treatment will be terminated after 48 weeks (End of Treatment [EoT]). The treatment period will be followed by a follow-up of 4 weeks' duration (End of Study [EoS]). Patients who enroll in Clinical Trial BT – L-CsA – 303 – FU (BOSTON-3) will forego the 4-week follow-up period of BOSTON-1 and will enroll directly into BOSTON-3 at the Week 48 Visit. For these patients, the EOT visit will be the EOS visit.

Any patients with ongoing SAEs will be followed-up until recovery or stabilization of the SAE. If a patient has enrolled in BOSTON-3, pharmacovigilance will be continuously assessed in the scope of the follow-up clinical trial.

Premature termination of clinical trial participation:

- Patients may discontinue participation in the clinical trial at any time by revoking their informed consent.
- The Investigator may withdraw a patient at any time if it is in the best interest of the patient based upon clinical assessments.
- Patient is lost to follow-up
- Re-transplantation. Patients who are eligible for and/or listed for re-transplantation will continue to participate in the trial until they receive re-transplantation surgery.
- Pregnancy (the patient will be followed via a pregnancy registry)
- Zambon SpA may choose to terminate the study at a site or as a whole for reasons such as, but not limited to, medical futility, safety concerns, or poor study site performance.

Patients stopping to take study treatment but not revoking their consent will be encouraged to continue the visits planned until the scheduled end and perform all the important safety and efficacy assessments for the full duration of the study.

If the patient to return for clinical follow-up, the patient will be contacted by telephone or a letter will be sent requesting a mandatory clinic visit and the reason for non-compliance will be documented.

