### 10.3.1 Procedures for Patient Withdrawal and Type and Timing of Data Collection

The patient is free to withdraw from the clinical trial for any reason and at any time without giving a reason for doing so and without penalty or prejudice. The Investigator is also free to terminate a patient's involvement in the clinical trial at any time if the patient's clinical condition warrants it and if it is in the best interest of the patient based upon clinical assessments.

If the subject decides to withdraw the consent or the Investigator decide to withdrawn a patient from the study, he/she should perform:

- End of Treatment Visit" (Visit 9) PRIOR to discontinuation, whenever possible (the reason for premature withdrawal should always be documented)
- A final clinical trial visit (Visit 10) at least 1 month after Visit 9, if possible

If a subject permanently discontinues study treatment or the Investigator decides to withdraw a subject from study treatment, this subject should be followed for additional outcome information provided that he/she maintains his/her consent to study participation. In other words, subjects should be encouraged to continue the participation in the clinical trial until the scheduled end, regardless of the treatment arm. Subjects should perform all study visits required by Study Protocol performing all important safety and efficacy assessments for the full duration of the Study

It is also possible that the Competent Authority(ies), IRBs/ECs or the sponsor request termination of the complete clinical trial, if there are concerns about conduct or safety.

Reasons for withdrawal are outlined in detail in [Section 9.6.1](#).

The reasons for withdrawal must be recorded in the eCRF.

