#### **12.1.4 Re-transplantation**

Re-transplantation is defined as the date that a patient undergoes lung re-transplantation surgery. The reason for re-transplantation will be recorded. At the time of re-transplantation, the patient will be withdrawn from the study.

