14.1 PRIMARY EFFICACY ANALYSIS

14.1.1 Analysis Population and Estimand

The primary endpoints will be analyzed using a “composite strategy” (International Conference on Harmonization (ICH) guideline E9 addendum on estimands and sensitivity analysis in clinical trials to the guideline on statistical principles for clinical trials). The estimand is defined by the following:

- Population: adult recipients of a single pulmonary allograft with clinically defined BOS, matching the inclusion and exclusion protocol criteria.
- Variable: FEV₁ data at Week 48 (visit 9) collected from the on site **CCI** spirometer (data collected with the **CCI** home spirometer will be used for supplementary analyses). Only accepted over-reader best FEV₁ data for the session from **CCI** will be used for analysis; data will not be re-derived.
- Intercurrent events: After IEs such as stopping treatment with L-CsA, augmentation of SoC therapy, etc., FEV1 measurements will still be collected and used in the analysis. In case of IEs preventing the use of FEV1 measurements, i.e. death and re-transplantation, the FEV1 will be imputed as treatment failure: FEV1 equal to zero for all visits subsequent the event. Rejected spirometries are those that did not meet the American Thoracic Society criteria; if rejected, then they would be re-done but there may be cases where they are rejected twice and resulting in missing data. Rejected spirometry is not an indicator of a better/worse outcome and can be assumed to be MAR.

- Population-level summary: difference in mean change from baseline in the FEV₁ at week 48 between treatment groups.

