14.2.3 PPS

The analysis will be conducted as described for the primary endpoint but will be performed on the PPS.

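### The per-protocol set keeps deaths by name but states no route in for patients withdrawn for re-transplantation, although the analysis it repeats scores both events as FEV1 = 0.

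*SAP*

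**What the plan says.** **Who is in the PPS.** SAP 9.2.3 takes patients in the full analysis set (FAS) who have no major protocol deviation and who either complete randomised treatment or are among those "who are withdrawn prematurely due to lack of efficacy or lack of tolerability of the clinical trial treatment". Both grounds for keeping a non-completer are then tied to the End Of Study form. For efficacy, "Lack of efficacy is defined by the withdrawn reason" of that same name on the form. For tolerability, the qualifying form reason is the one that opens "Adverse Event (Including SAE/Death". A death recorded under that reason therefore stays in.

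**Re-transplantation.** Protocol 12.1.4 states: "At the time of re-transplantation, the patient will be withdrawn from the study". Protocol 9.6.1 gives re-transplantation its own bullet among the grounds for premature termination and adds: "Patients who are eligible for and/or listed for re-transplantation will continue to participate in the trial until they receive re-transplantation surgery". Protocol 10.3.1 refers the reader there: "Reasons for withdrawal are outlined in detail in" Section 9.6.1.

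**Scoring.** SAP 14.1.1 uses a composite strategy in which death and re-transplantation both count as treatment failure, with "FEV1 equal to zero for all visits subsequent the event". SAP 14.1.3 builds this into the primary mixed model.

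**The PPS run.** SAP 14.2.3 says: "The analysis will be conducted as described for the primary endpoint but will be performed on the PPS".

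**The concern.** The primary analysis treats death and re-transplantation as the same kind of failure. The PPS definition names the first and is silent on the second. If a re-transplanted patient is recorded under any other form reason, the zero that SAP 14.1.1 assigns never reaches the PPS model, while the zero for a death does.

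That exclusion would be decided by something that happens after randomisation and that the plan itself scores as an outcome. It would flatter the arm with more re-transplantations. SAP 9.1 uses the choice of analysis population to judge robustness, so a gap between the FAS and PPS results could come from this definition rather than from deviations or ordinary drop-out.

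The silence looks like an alignment gap. The two PPS bullets match Protocol 15.1, which sits beside an estimand (Protocol 15.2.3.1) that modelled death and re-transplantation as if they had not happened. SAP version 3.0 moved to the composite strategy, and its version history lists the sections affected. Neither 9.2.3 nor 14.2.3 is among them.

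**Working it through.** **1. Tracing each event through the plan**

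| Step | Death before Week 48 | Re-transplantation before Week 48 |
|---|---|---|
| Completes treatment as scheduled? | No | No; withdrawn at surgery (Protocol 12.1.4) |
| Retained form reason (SAP 9.2.3)? | Yes, named in the adverse-event reason | None stated |
| Score in the primary model (SAP 14.1.1, 14.1.3) | FEV1 = 0 | FEV1 = 0 |
| Score in the PPS run (SAP 14.2.3) | FEV1 = 0 | FEV1 = 0 if in the set; absent if not |

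Nothing in SAP 9.2, 14.2.3 or 16 brings re-transplanted patients back in. The blinded data review meeting in SAP 9.2 is described as deciding PPS exclusions for major deviations, not as adding patients whom the definition leaves out.

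**2. The planning figure used as a yardstick**

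Inputs from SAP 8.2: difference 200 mL, SD 350 mL, one-sided alpha 0.025, power 80%. The normal approximation gives n = 2 × (1.960 + 0.842)² × (350/200)² = 48.1, so 49 per group. With the noncentral t distribution, power is 0.800 at 49 and 0.808 at 50 per group. The stated 50 per group reproduces.

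**3. Illustrative size of one exclusion**

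From the documents: 62 patients randomised (SAP 8.2) at 1:1, taken as 31 per arm because the actual split is not given. Assumed, because the documents give no values: baseline FEV1 *B* of the re-transplanted patient, and mean change *m* in the rest of the arm.

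A patient scored FEV1 = 0 has a change of -*B*. With that patient in, the arm mean is (30*m* - *B*)/31; with the patient out, it is *m*. Exclusion therefore raises the raw arm mean by (*B* + *m*)/31.

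With *m* = -0.2 L:
- *B* = 1.0 L: 0.8/31 = 25.8 mL (13% of 200 mL)
- *B* = 1.4 L: 1.2/31 = 38.7 mL (19%)
- *B* = 1.8 L: 1.6/31 = 51.6 mL (26%)

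Wider assumptions (*B* from 1.0 to 2.0 L, *m* from -0.2 to -0.5 L) run from 0.5/31 = 16 mL to 1.8/31 = 58 mL.

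For scale, the 95% confidence half-width for a difference of two means with 31 per arm and SD 350 mL is about 178 mL. The shift in the treatment difference is the difference between the two arms' shifts, so equal numbers of exclusions at similar baselines roughly cancel.

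**The case against.** **The form is not in the documents.** A reader might infer from Protocol 9.6.1 that re-transplantation is a separate form reason, and hence that these patients are certainly dropped. The documents do not support that. The 9.6.1 list contains neither of the two reasons that SAP 9.2.3 takes from the form, and it does not list death, so it cannot be the form's list. A site could reasonably record re-transplantation as lack of efficacy, since SAP 14.1.1 itself calls it treatment failure. This stands: exclusion is conditional on coding. It does not remove the point, because membership then rests on a site's choice of label rather than on a rule.

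**A PPS is meant to differ from the FAS.** SAP 9.2.3 gives its purpose as assessing the impact of drop-outs and major deviations, so removing some non-completers is expected. That is fair as far as it goes, but it does not explain keeping one of two identically scored failures and saying nothing of the other.

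**Reasons for re-transplantation may vary.** Protocol 12.1.4 has the reason recorded, so not every case need reflect the disease under study. True, but the primary analysis scores every re-transplantation as failure whatever its reason, and Protocol 12.1.2 counts it as BOS progression.

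**Little depends on this analysis.** The FAS is all randomised patients, and the ANCOVA and t-test also apply the zero. SAP 9.2.3 says only that the PPS may be used, SAP 14 calls all analyses descriptive, and Protocol 15.2.3.1 expects such events to be rare. All of this stands and limits the severity.

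**Conclusion.** The definition has a gap: deaths have a named route into the PPS and re-transplantations have none. Whether any patient is lost depends on how the End Of Study form was completed. If any is lost, the exclusion depends on outcome and favours the arm with more re-transplantations.

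The 26–52 mL per excluded patient is a raw-mean illustration. It rests on an assumed baseline of 1.0–1.8 L, an assumed mean change of -0.2 L in the others, 31 per arm and no other PPS exclusions. The planned analysis is an adjusted spline mixed model with random effects, so its shift could differ. The documents give no count of re-transplantations; with none, there is no effect.

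A reader might go further and infer that the primary result is compromised, or that the PPS is tilted towards L-CsA. Neither follows. The FAS analysis keeps both events, and the direction depends on which arm has the re-transplantations. Severity is minor.

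**What to change.** In the first bullet of SAP 9.2.3, add: 'or who are withdrawn because of re-transplantation, whatever End Of Study reason is recorded'. In 14.2.3, state that the FEV1 = 0 scoring of 14.1.3 applies to these patients in the PPS analysis. Report the number of re-transplantations by arm beside the PPS result.

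The cost is a clause, a sentence and a count. No new data are needed, and the primary analysis does not change. If the form already places every re-transplantation under a retained reason, PPS membership will not change either, but the rule will no longer depend on coding.

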#### **10.3.3 Follow-up of Withdrawn Patients**

Patients stopping to take study treatment but not revoking their consent will be encouraged to continue the visits planned until the scheduled end and perform all the important safety and efficacy assessment for the full duration of the study.

All patients withdrawn from the clinical trial prematurely will be followed for AEs and SAEs for a further 4 weeks. Any patient with ongoing SAEs will be followed until recovery or stabilization of the SAE.

The 4-week safety follow-up will be obsolete if a patient completes participation in the clinical trial and consents to participate in Clinical Trial BT – L-CsA – 303 – FU (BOSTON-3). In this case, safety will be continuously assessed in the scope of the follow-up clinical trial.

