10 DISPOSITION

The number of patients screened, failed screening (patients who did not meet all eligibility criteria and was not randomized), enrolled (patients with informed consent and all eligibility criteria met or randomized), treated but not randomized, randomized (treated, and not treated with clinical trial treatment), completing clinical trial treatment (and reasons for not completing), and completing the clinical trial (and reason for not completing) will be presented in frequency tables by treatment group.

The number of patients in each analysis population (SAF, FAS, and PPS) will be summarized by treatment group. A by-patient listing of disposition will be provided.

All major protocol deviations will be presented as a frequency table by treatment group and in a by-patient listing for all randomized patients, which will include the category of the deviation, the deviation text, and whether the patient was excluded from PPS.

In addition, the counts on major COVID-19 related PDs will be provided, together with a by-patient listing for all COVID-19 related PDs.

In addition, a listing of the patients affected by Coronavirus Disease of 2019 (COVID-19) and their COVID-19 AE details will be provided for the FAS.

A table for the summary of stratification factors by treatment group for FAS and a separate listing of patients with mis-stratifications will be displayed.

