14.2.5.1 Patients impacted by COVID-19 pandemic

The analysis of primary endpoint will be performed using the LMM described in the primary analysis with the inclusion of additional categorical covariates:

- A binary covariate representing if patients have been affected by COVID-19 during the treatment period:
 - Affected, if an AE of COVID-19 is reported in the eCRF AE page between randomization and date of study completion/premature discontinuation/withdrawal of informed consent in the EOS page.;
 - Not affected, if no AEs of COVID-19 are reported in the eCRF AE page between randomization and date of study completion/premature discontinuation/withdrawal of informed consent in the EOS page..
- A binary covariate representing if patients have been randomized before or after the COVID-19 pandemic outbreak:
 - Before, if date of randomization is before 11 March 2020;
 - After, if date of randomization is equal or after 11 March 2020.

FEV₁ data will be descriptively summarized by impact of COVID-19 (COVID-19 affected vs Not COVID-19 affected, and randomized before COVID-19 Pandemic Outbreak vs randomized after COVID-19 outbreak) at each visit, by treatment and overall. The treatment comparison for difference in mean change from baseline in the FEV₁ at week 48 will be carried out using t-tests as described in section 14.2.2, including both newly created binary covariates. This will also be performed for each of the subpopulations defined by the binary covariates above i.e. patients affected/not affected by COVID-19 during the treatment period and patients randomized before/after the COVID-19 pandemic outbreak.

Furthermore, it is of interest to categorize each visit for each patient to assign these before or after the COVID-19 pandemic outbreak. A summary table will be produced to descriptively display the effects of FEV₁ over time by taking each visit with respect to the COVID-19 outbreak pandemic

L-CsA:

Treatment of BOS after SLT

Protocol Number:

BT – L-CsA – 301 – SLT

Sponsor:

Zambon SpA

date into consideration. The treatment comparison for difference in mean change from baseline in the FEV₁ at week 48 will be analyzed similarly using the t-test as described in section 14.3 for both groups, visits before COVID-19 pandemic outbreak, visits after COVID-19 pandemic outbreak.

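### The per-protocol rule takes its withdrawal reason from the End Of Study form, so L-CsA patients who stop the drug but stay in follow-up appear to drop out of the PPS, with essentially no SoC counterpart

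*SAP*

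**What the plan says.** SAP 9.2.3 builds the PPS from FAS patients without major deviations "who complete randomized treatment as scheduled or who are withdrawn prematurely due to lack of efficacy or lack of tolerability of the clinical trial treatment". It then makes the second limb operational: "Lack of tolerability is defined by the withdrawn reason" of adverse event, serious events and death included, entered on the End Of Study form. Lack of efficacy is read from the same form in a parallel sentence. No other source is named.

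That form works at study level. Protocol 10.3 has it completed when a patient is withdrawn, and SAP 14.2.5.1 uses it for the date of "study completion/premature discontinuation/withdrawal of informed consent in the EOS page".

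The protocol separates stopping the drug from leaving the trial. Section 9.6.1 says: "Patients stopping to take study treatment but not revoking their consent will be encouraged to continue the visits planned until the scheduled end". Sections 10.3.1 and 10.3.3 repeat the request, and 10.3.4 counts a patient followed through Visit 9 as having completed the trial, with no condition on still taking the drug.

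Treatment-level reasons do exist. Protocol 9.4.3 requires the date and reason for stopping L-CsA on the case report form. SAP 10 tabulates patients "completing clinical trial treatment (and reasons for not completing") separately from those completing the trial. The PPS rule does not use these reasons.

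**The concern.** Two patients stop L-CsA for the same adverse event. One leaves the trial with that reason on the End Of Study form and is in the PPS. The other does as the protocol asks and attends to Week 48. The second patient has not completed randomized treatment and has no withdrawal reason on the form, so appears to fail both limbs. PPS membership then turns on whether the patient agreed to follow-up, not on why treatment stopped.

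The route is close to one-sided. SAP 15.2.2 ends the SoC period only at study completion or early termination, so an SoC patient followed to Week 48 has, in effect, completed treatment.

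What is at stake is the PPS as a robustness check. SAP 9.2.3 gives it the job of showing the impact of drop-outs and major deviations, and SAP 9.1 relies on comparing analysis populations. A set that loses treatment discontinuers selectively from one arm is poorly suited to that job.

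**Working it through.** **Tracing the rule**

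| Patient | Completed randomized treatment? | Withdrawal reason on End Of Study form? | In PPS? |
|---|---|---|---|
| L-CsA, stops for adverse event or inefficacy, leaves trial | No | Yes | Yes |
| L-CsA, stops for the same reason, followed to Week 48 | No | Apparently none (Protocol 10.3.4) | Apparently no |
| L-CsA, stops, stays for a time, then leaves for an adverse event or dies | No | Yes | Yes |
| SoC, followed to Week 48 | Yes, on SAP 15.2.2 | Not needed | Yes |

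**Yardstick.** The point rests on no figure in the plan, but the design values give a scale: a 200 mL difference, SD 350 mL, one-sided 0.025, at least 80% power with 50 per arm (Protocol 15.5, SAP 8.2). Check by normal approximation: n = 2 × (1.960 + 0.842)² × (350/200)² = 2 × 7.85 × 3.0625 = 48.1, so 49 per arm. The exact t-test power at 50 per arm is 80.8%. The stated figure reproduces.

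**Size of a possible shift.** SAP 8.2 reports 62 randomized; 31 per arm is assumed from 1:1 allocation. Let k be the number of L-CsA patients excluded by this route, f = k/31, and d the amount (mL) by which their mean FEV1 change is worse than that of the other L-CsA patients. With them in, the L-CsA mean is m − f × d; without them it is m. The shift in the treatment difference is therefore f × d, positive meaning toward L-CsA. Both k and d are assumptions, because the documents give neither. The formula is for a simple comparison of means; the mixed model would give a similar but not identical figure.

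| k | f | d = -100 | d = 0 | d = 100 | d = 300 |
|---|---|---|---|---|---|
| 1 | 0.032 | -3.2 | 0 | 3.2 | 9.7 |
| 3 | 0.097 | -9.7 | 0 | 9.7 | 29.0 |
| 6 | 0.194 | -19.4 | 0 | 19.4 | 58.1 |

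The largest value is 58.1/200 = 29% of the design effect. The standard error of the difference at 31 per arm is 350 × √(2/31) = 89 mL, so even that shift is about 0.65 of a standard error.

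**The case against.** The strongest objection concerns direction. A reader might infer that the rule strips intolerant or failing patients from the L-CsA arm and so favours the drug. The documents do not support that. Nothing in them says how patients who stop but stay fare on FEV1. The rule keeps those who leave for an adverse event or inefficacy. It also keeps deaths, which enter as FEV1 of zero because SAP 14.2.3 runs the PPS analysis like the primary one. The excluded patients are alive and attending at Week 48. A shift toward L-CsA is plausible: the rule also governs inefficacy, and Protocol 10.3.1.1 treats a symptomatic FEV1 fall as intolerance, though that concerns acute response to dosing. Plausible is as far as it goes.

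Second, the eCRF is not visible. Protocol 14 and SAP 9.5.1 speak of patients who prematurely discontinue trial participation yet are encouraged to complete follow-up. Such a patient might have an adverse-event reason on the form while still attending, and would be kept. This is possible but sits badly with Protocol 10.3.4. It is why the conclusion says these patients appear to fall outside the PPS.

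Third, SAP 8.1.2 counts SoC alone as treatment, and Protocol 15.2.2 plans discontinuation reasons for both treatments. Neither says how a patient stops SoC while remaining in the trial, and SAP 15.2.2 leaves almost no room for it.

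Fourth, leaving long off-drug follow-up out of a per-protocol set is a defensible choice. But the rule does not make that choice consistently, since it admits people who stopped for the same reasons and left.

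Finally, the blinded data review meeting settles set membership (SAP 9.2). No text lets it override the form-based definition.

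**Conclusion.** The inconsistency stands. On the current wording, L-CsA patients who stop for lack of efficacy or tolerability and stay in follow-up appear to be excluded, those who stop for the same reasons and leave are kept, and SoC has essentially no equivalent. The PPS comparison can be biased as a result, but the direction is conditional on how the excluded patients fare. With 31 per arm, 1 to 6 exclusions and a difference of -100 to 300 mL, all assumed, the shift lies between 19 mL against L-CsA and 58 mL toward it. It is zero if the excluded patients do no differently.

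The consequence is confined to the PPS. The FAS is all randomized patients (SAP 9.2.2) and keeps FEV1 after the drug is stopped (SAP 14.1.1). The PPS is supplementary, and SAP 14 makes every analysis descriptive. The rule should be corrected, but no primary conclusion depends on it.

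**What to change.** In SAP 9.2.3, define lack of efficacy and lack of tolerability from the recorded reason for stopping trial treatment, whatever the patient's study-completion status. Use the End Of Study reason only where treatment and study ended together. Add a sentence saying what completing randomized treatment means in the SoC arm. Settle both before the blinded data review meeting.

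The cost is a few lines of SAP text and a change of source variable. No new data are needed, since the reasons are already required by Protocol 9.4.3 and tabulated under SAP 10. The one drawback is that the PPS would then contain some off-drug FEV1 and move closer to the FAS. In exchange, patients who stop for the same reason are treated alike.
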